Our telehealth intervention, based on the Family Check Up (FCU) focuses on supporting parents by increasing parenting self-efficacy, stress management skills, self-regulation skills, and sleep routines, which are hypothesized to lead to the prevention of opioid misuse and OUD as well as improve mental health and increase responsive parenting. The FCU has been tested in more than 25 years of research, across multiple settings, and is an evidence-based program for reducing high-risk behavior, enhancing parenting skills, and preventing substance use through emerging adulthood (Connell et al. 2007; Dishion et al., 2008; [name], Connell & Dishion et al., 2009; [name] et al., 2011; [name] et al., 2018). It is named in NIDA's "Principles of Substance Use Prevention for Early Childhood" as one of only three effective selective prevention programs for substance abuse among families with young children. The FCU has also been endorsed as an evidence-based practice by the Maternal Infant and Early Childhood Home Visiting Program (MIECHV), and has been listed as a promising program by the Blueprints for Healthy Youth Development since 2013 (Paulsell et al., 2010). Most recently, the FCU was adapted to be delivered to parents in a web-based format (protocol: 07032014.004). The current project aims to address barriers of access to prevention services by delivering the FCU in a telehealth model.

B. Specific Aims/Study Objectives

The overarching aims of the study include:

Specific Aim 1. Working with community stakeholders in rural Oregon to expand the FCU Online to target early childhood (18mo-5 years) and mothers with histories of substance use.

Specific Aim 2. Examine the efficacy of the FCU Online for Oregon families with:

- a) Parents with young children (18mo-5 years) who have a history of opioid use and addiction (n=300)
- b) Parents with young children (18mo-5 years) who have a history of substance misuse and/or depression (n=100).

Specific Aim 3. Examine factors related to successful uptake and implementation of the FCU telehealth model.

For the first phase of the study (April 2020- April 2021), we will be focusing on Specific Aim 1 by conducting focus groups with stakeholders. For the second phase of the study (summer 2021) we will pilot the FCU Online with 10 families so that we may fine tune recruitment procedures, screening criteria, acceptability of phone interviews and

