Supervision and limit setting: Parents are given information and practice opportunities for managing behavior in toddler years, ignoring unwanted behavior, setting limits, and keeping the home a safe environment.

Consumer Satisfaction/Exit Interview The 2-page website feedback survey administered at the end of the pilot study asks questions about acceptability, usability of the FCU Online as well as questions about working with a Family Consultant, and suggestions for improvement to the study procedures/content (see attachment "Rural Opioid website satisfaction survey and exit interview"). The consumer satisfaction/exit interview will take approximately 20 minutes.

3. Clinical trial research study (n=400 parents).

After incorporating feedback from the pilot study to materials and process, we will begin the clinical trial phase of the study, where we will recruit 400 English or Spanish speaking families with a child between the ages of 18 months and 5 years old. Two hundred families will be randomly assigned to an intervention condition where participants complete four phone interviews/ surveys over the course of a year and receive the FCU along with coaching from a Family Consultant; two hundred families will be randomly assigned to a control condition where participants complete four phone interviews/surveys over the course of a year and are given access to the FCU at the conclusion of their study participation (e.g., one year later). A quick completion bonus of \$25 will be offered to families at each wave of data collection, if they complete a phone interview or survey within 2 weeks of it being offered to them. Families in the control condition will not receive coaching from a Family Consultant. All families will also be invited to opt into using the EARS tool, which is installed on the participant's phone and collects passive data to record naturalistic behavior related to mental health. Parents will have the opportunity to receive up to \$425 in one year for participating in the study or up to \$400 if they opt out of the EARS component. All research activities will be available to be conducted in either English or Spanish, depending on the preference of each family.

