We will assess participant quantitative ratings during the usability testing phase in which the benchmark for acceptable ratings will be mean ratings of 4 or greater on a 5-point scale for each of the SUS items and an overall SUS rating of 80.3, which represents an "A" score. Program acceptability will also be demonstrated by (a) a high level of program usage (e.g., 80% of participants complete the FCU assessment and feedback sessions), and (b) a high degree of consumer satisfaction (e.g., mean ratings > 4 on a 5-point rating scale across satisfaction domains).

AIM 2. EXAMINE THE EFFICACY OF FCU ONLINE FOR RURAL FAMILIES WITH OPIOID USE: MAIN EFFECTS, MEDIATORS, AND MODERATORS.

RESEARCH HYPOTHESES. The hypotheses tested in this aim are (a) families in the intervention condition will show significant improvements on the primary outcomes (child problem behavior and school readiness) and secondary outcomes (parenting skills, parent self-regulation/executive control, and child self regulation/ executive control), compared with families in the control condition; and (b) the putative intervention mechanisms of parenting skills and child self-regulation will mediate (either partially or fully) the association between study condition and the longitudinal trajectories of the primary outcomes. Though we have no specific hypotheses regarding moderating mechanisms, we will also conduct exploratory analyses to examine potential moderators of intervention effects. See Statistical Design component of this proposal for additional information.

We will test whether change in the putative mediating mechanisms of parenting skills and self-regulation (e.g., baseline to 3 months) mediate the association between study conditions and longitudinal trajectories of the primary child outcomes (e.g., overall trajectories, 3- to 12-month change to establish temporal precedence of mediators). Such mediating effects will be tested using the strategies outlined by MacKinnon and Preacher and Hayes. We will assess the joint significance of the indirect pathways (i.e., the joint significance of the pathways from the predictor to the mediating variable and from the mediating variable to the outcome) using the bias-corrected bootstrap test, as recommended by Fritz and MacKinnon. We will also use the bootstrapping technique to test multiple simultaneous mediators proposed by Preacher and Hayes.

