The moderation analyses will follow recommendations by Kraemer and colleagues and analytic methods of Aiken and West, Jaccard and Turrisi, and Preacher et al. Each of the potential moderating effects (e.g., child biological sex, race/ethnicity, SES, service utilization; and neonatal abstinence syndrome) will be investigated by conducting the above-mentioned mixed-effects analyses for each outcome that incorporate the Moderator \times Condition interaction term. We have no specific hypotheses for testing sex as a biological variable that would impact outcomes, but we will include sex as a moderator in these analyses. For example, we will test for individual differences in the effect of intervention response (e.g., child problem behavior trajectories) as a function of the participant's value of baseline moderator. Significant moderating effects will be further probed to understand the nature of the conditional relation using computational tools recommended by Preacher et al.

SAMPLE SIZE AND POWER. Using an intent-to-treat approach for the hypothesis of an overall intervention effect, with 127 participants per condition after accounting for 15% attrition across the 12-month assessment period, alpha set to .025 (to adjust for the two outcome domains), there is sufficient power ($>.80$) to detect a condition effect of Cohen's d = .30 or larger. Previous FCU efficacy trials have demonstrated medium-to-large effects for antisocial cigarette use, alcohol use, cannabis use, antisocial behavior, and family conflict. As reported in the prior research section, initial analyses of our ongoing efficacy trial of the FCU Online program demonstrated a medium effect size ($d = .45$) for improvements in child health behaviors, and small-to-medium effect sizes for child social/emotional behavior ($d = .35$), parenting self-efficacy and confidence ($d = .37 - .41$). Given that the effect sizes obtained in the previous FCU efficacy research and the FCU Online preliminary analyses are larger than the power estimates, we should be sufficiently powered to detect meaningful differences between study conditions.

AIM 3. EXAMINE FACTORS RELATED TO SUCCESSFUL UPTAKE AND IMPLEMENTATION.

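### The two primary outcomes appear to share alpha by an equal .025 split; Holm's step-down test keeps the same 5% family-wise error and is more powerful when both effects are real

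*SAP*

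**What the plan says.** The research hypotheses under SAP Aim 2 predict that intervention families will show "significant improvements on the primary outcomes (child problem behavior and school readiness", so there are two primary outcomes. The sample size and power paragraph of the same Aim sets "alpha set to .025 (to adjust for the two outcome domains". Since .05/2 = .025, this is an equal (Bonferroni) split. The paragraph plans "with 127 participants per condition after accounting for 15% attrition across the 12-month assessment period" and concludes that "there is sufficient power ($>.80$) to detect a condition effect of Cohen's d = .30 or larger".

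The .025 appears nowhere else. Neither document mentions a stepwise or gatekeeping procedure, or gives a threshold for declaring success on a primary outcome. The Aim 2 hypotheses refer to a Statistical Design component of the proposal, which is not part of the published SAP.

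**The concern.** If each outcome must reach p < .025 whatever the other shows, power on the second outcome is given up with no gain in family-wise error control. For example, take p = .001 for problem behavior and p = .04 for school readiness. Under a fixed split, school readiness is called negative. Under Holm, the first p-value passes .025, the second is then judged at .05, and both are declared with family-wise error still at most 5%. The Aim 2 hypothesis concerns both primary outcomes, and the loss falls on that joint claim.

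**Working it through.** **Inputs.** From SAP Aim 2: two primary outcomes, alpha .025 each, d = .30, 127 per arm, power above .80. Assumed, because the SAP does not say: two-sided tests (the Aim 3 power paragraph is two-tailed); equal effects on both outcomes; correlation between the two test statistics, r, from 0 to .7.

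**The SAP's own figures.** Attrition agrees with 300 enrolled: 150 × .85 = 127.5. The expected z statistic in a simple two-sample comparison is .30 × √(127/2) = 2.391. The two-sided .025 critical value is 2.241, so power is Φ(2.391 − 2.241) = Φ(.149) = .56. The stated figure above .80 is not reproduced this way. It can be reached with an unstated gain from baseline adjustment or repeated measures, for example a single-endpoint ANCOVA with baseline correlation of about .63. The Protocol randomizes 200 per arm, and 200 × .85 = 170 gives .70 unadjusted. I therefore show results from both .80 and .56.

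**Formulas.** Let c1 = 2.241 (alpha .025) and c2 = 1.960 (alpha .05), both two-sided. Let m be the expected z for each outcome: 2.241 + .842 = 3.083 at .80 power, and 2.391 at .56. The opposite tail is negligible.

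- Split, per outcome: P(z1 > c1).
- Extra under Holm: e = P(c2 < z1 < c1 and z2 > c1).
- Holm, per outcome: split power + e.
- Holm, both outcomes: P(both > c1) + 2e.
- At least one: 2 × per-outcome split power − P(both > c1), the same under both rules.

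**By hand at r = 0, power .80.** P(z1 > 1.960) = Φ(3.083 − 1.960) = .869, so P(c2 < z1 < c1) = .869 − .800 = .069. Then e = .069 × .80 = .055. Per-outcome power is .80 + .055 = .855. Power for both goes from .80² = .64 to .64 + 2 × .055 = .75.

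**Across correlations** (bivariate normal):

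| Base power at .025 | r | Per outcome, Holm | Both, split | Both, Holm | At least one, either rule |
|---|---|---|---|---|---|
| .80 | 0 | .855 | .640 | .751 | .960 |
| .80 | .3 | .850 | .666 | .766 | .934 |
| .80 | .5 | .846 | .687 | .778 | .913 |
| .80 | .7 | .841 | .713 | .794 | .887 |
| .56 | 0 | .619 | .313 | .433 | .806 |
| .56 | .3 | .616 | .360 | .473 | .758 |
| .56 | .5 | .613 | .395 | .503 | .724 |
| .56 | .7 | .610 | .434 | .535 | .684 |

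**Only one effect real (r = 0).** The real effect gains only when the null outcome is falsely rejected at .025. From .80 power the gain is .069 × .025 = .002, giving .802. From .56 it is .107 × .025 = .003, giving .562. The error on the null outcome rises from .025 to .025 + .025 × .80 = .045 (.039 from .56 power), still below .05.

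**No effect real.** Both rules give the same family-wise error: 1 − .975² = .049 at r = 0, and less at positive r.

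**The case against.** The strongest objection is that the SAP never says the outcomes will be judged at .025. The figure is the alpha of a power calculation, and planning at .025 is compatible with testing by Holm later. This stands in part. A reader might infer that the plan commits to a fixed .025 rule, under which p = .04 on the second outcome must be called negative. The documents do not support that: it is the natural reading of the only adjustment given, but still an inference, and the Statistical Design component might hold a rule. If no rule exists, one is needed anyway.

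Second, the SAP speaks of domains and does not fix an instrument, timepoint or contrast for either primary outcome. Holm needs one p-value per outcome. This stands, and the fix has to cover it.

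Third, the gain assumes that both effects are real, and the power paragraph cites no earlier effect size for school readiness. This also stands. A reader might infer that Holm improves the trial's overall chance of a positive result, or that it rescues the power claim. It does neither: the chance of at least one significant outcome is identical, and from a base of .56 per-outcome power reaches only .62.

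Fourth, an equal split is valid and comes with simple matching intervals. That is true, and it is why this is an improvement and not a correction.

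Finally, timing. The SAP is dated 9.20.2019, the Protocol is dated 4.18.2025, and the trial was scheduled to start in fall 2021. The documents do not say whether outcomes have been analyzed. If they have been compared by condition, moving to Holm would be a post hoc loosening of the criterion.

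**Conclusion.** The point holds as a cheap improvement. The equal split is valid and nothing in it inflates error. Holm rejects everything the split rejects, keeps family-wise error at 5% under any dependence, and needs no more participants.

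With two equal real effects, two-sided tests and correlation 0 to .7, the gain is about 4 to 6 points per outcome. For significance on both outcomes it is 8 to 11 points from the SAP's .80 power, or 10 to 12 points from the unadjusted .56. With only one real effect it is at most about 0.3 points. That Holm is never worse does not depend on these assumptions; only the size of the gain does.

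A reader might call the change free. It is free in family-wise error and sample size, but it has the small costs given with the fix.

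**What to change.** Add to SAP Aim 2, before outcomes are compared by condition: (1) the single primary test for child problem behavior and the single primary test for school readiness, each with its instrument, timepoint and contrast; (2) a statement that the two p-values are judged by Holm's step-down procedure at overall two-sided .05. Keep .025 as the conservative planning alpha, so the sample-size paragraph need not change on this account. If outcomes have already been compared by condition, keep the .025 threshold and label any Holm result as post hoc.

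The cost is a few sentences and two small trade-offs. Simple 97.5% simultaneous intervals will not always match the Holm decisions; they can still be reported alongside, with that noted. The error on a single true null can rise above .025 but stays within .05.

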Official Title: "Rural Families Affected by Opioid Use: An Online Parenting Intervention"

And

"Supplement to Prevention Research Center: Parenting Among Women Who are Opioid Users, Project 2"

NCT Number: NCT05180487

Document Date: 9.20.2019

Document: Statistical Analysis Plan

DATA MANAGEMENT AND ANALYSIS

Data analyses and management will be supported in collaboration with the Data Science Core of the PWO Prevention Center, and will rely on resources and support from the center to test complex models associated with the specific aims of the project as well as management of data in the context of the larger dataset associated with the Center. Data management systems similar to those used in our other web-based research projects will be used to ensure the integrity of the analytic results. These systems entail the creation of scheduling algorithms and web-based data collection forms for each instrument. The collection system contains backup and protection routines that ensure confidentiality and preservation of the electronic records.

We will use accepted practices for handling missing data when appropriate. Maximum likelihood methods with time as a random variable, such as the mixed-effects regression models described below, allow the use of all available data and reduce bias associated with attrition and increasing power. These procedures can provide unbiased conclusions even with substantial attrition. We anticipate a participation rate through 12-month follow-up of at least 85% based on our previous FCU school-based efficacy trials and our current rate of participation and retention in our FCU Online randomized trial.

We will compare baseline characteristics of participants across conditions to test for significant differences; characteristics that differ across conditions will be used as covariates in subsequent analyses. Logistic regression analyses will be used to examine potential differences by study condition between dropouts and continuing participants on baseline measures. Attrition analyses will provide information about the external validity of the study, and interaction effects between condition and predictors will provide information about potential confounding effects.

AIM 1: WORK WITH COMMUNITY STAKEHOLDERS IN RURAL OREGON TO EXPAND THE FCU ONLINE TO TARGET EARLY CHILDHOOD (AGES 2-5) AND MOTHERS WITH OPIOID USE AND ADDICTION.

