RESEARCH HYPOTHESES. We will assess the feasibility of the FCU as an Internet-delivered intervention in rural communities with high levels of opioid use, including the extent to which participants engaged in the intervention, completed the program, and were satisfied with the program. We hypothesize that the FCU Online intervention will demonstrate feasibility based on benchmark analyses described below. We also hypothesize that website usage (dosage) and coach fidelity will be associated with significantly greater change in the primary and secondary outcomes.

SAMPLE SIZE AND POWER. With a sample size of 127 in the intervention condition (accounting for 15% attrition), with alpha set to .05 (two-tailed), there is sufficient power ($>.80$) to detect $r = .25$ (moderate effects) for the process analyses involving treatment acceptability, fidelity, and engagement.

Data Management and Analysis for Supplement Pilot Aim

Data management systems similar to those used in our other web-based research projects will be used to ensure the integrity of the analytic results. These systems entail the creation of scheduling algorithms and web-based data collection forms for each instrument, including backup and protection routines that ensure confidentiality and preservation of the electronic records. We will use accepted practices for handling missing data when appropriate. Maximum likelihood methods with time as a random variable, such as the mixed effects regression models described below, allow the use of all available data and reduce bias associated with attrition and increasing power. These procedures can provide unbiased conclusions even with substantial attrition. We anticipate a participation rate through three months of at least 85% based on our previous FCU school-based efficacy trials and our current rate of participation and retention in our FCU Online RCT (90%).

Aim 1: Adapt the FCU Online for young adult parents with a history of substance misuse using a prevention framework

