Usability. We will assess participants' quantitative ratings during the usability testing phase in which the benchmark for acceptable ratings will be mean ratings of 4 or greater on a 5-point scale for each of the System Usability Scale (SUS) items and an overall SUS rating of 80.3, which represents an "A" score. Program acceptability will also be demonstrated by (a) high level of program usage (e.g., 80% of participants complete the FCU assessment and feedback sessions), and (b) high degree of consumer satisfaction (e.g., mean ratings > 4 on a 5-point rating scale across satisfaction domains).

Aim 2: Conduct a pilot test of the efficacy of the adapted FCU Online developed in Aim 1.

Statistical design. Individual participants will be randomized to condition and will therefore be the unit of analysis in tests of condition effects in all statistical models. The pilot study will use a pre-post between-group design to examine differences between conditions in the intervention targets assessed at baseline and postintervention (3-month assessment point). Due to the limited sample size and duration of the pilot study, we do not expect to find differences between conditions for the more distal outcomes of opioid misuse or OUD.

Intervention effects and statistical power. We expect that participants receiving the FCU Online intervention will demonstrate improvements in the intervention targets compared to those assigned to the treatment-as-usual control condition. We will examine descriptive statistics and pre-post data to evaluate trends and outcomes, which will provide us with preliminary data to support further research with this population. Mixed-effects regression models will be used to examine post-test differences in the intervention targets between

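### Is the Aim 2 power claim (>.80 for d = .30 with 127 per condition) wrong because a plain two-group calculation on the same figures gives .555?

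*SAP*

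**What the plan says.** The SAP's Aim 2 paragraph on sample size and power gives its inputs as "with 127 participants per condition after accounting for 15% attrition across the 12-month assessment period, alpha set to .025", the halved alpha being for two outcome domains. From these it states that "there is sufficient power ($>.80$) to detect a condition effect of Cohen's d = .30 or larger". It then cites prior FCU Online effects of d = .35, .37 to .41 and .45, and concludes that the prior effects "are larger than the power estimates, we should be sufficiently powered to detect meaningful differences between study conditions".

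The analysis model is mentioned in three places:

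- The SAP's opening section on data management and analysis refers to "Maximum likelihood methods with time as a random variable, such as the mixed-effects regression models described below", and says these use all available data.
- The Aim 2 hypotheses end with "See Statistical Design component of this proposal for additional information".
- The moderation paragraph speaks of "conducting the above-mentioned mixed-effects analyses for each outcome".

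The protocol (section C, clinical trial research study) schedules assessments at baseline, 3 months, 6 months and 1 year.

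The SAP's other power statements give more detail. Aim 3 reads "with alpha set to .05 (two-tailed), there is sufficient power". The supplement pilot names its contrast: "Mixed-effects regression models will be used to examine post-test differences in the intervention targets between" the two conditions, controlling for baseline, at a two-tailed alpha of .05.

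**The concern.** A reader who enters n = 127, d = .30 and alpha .025 into a standard two-sample calculation does not get .80, or anything near it. Dropout does not explain the gap, because 150 per condition with no loss still gives only .635 two-sided or .736 one-sided. Leaving out the alpha split gives .663 two-sided at 127.

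The detectable effect on this reading, d = .389, is also larger than two of the effects the SAP cites in support (.35 and .37). The conclusion of sufficient power would then be partly contradicted by its own evidence.

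The model that could close the gap is announced as described below in one place and as above-mentioned in another, but no Aim 2 main-effect model appears between them. If the claim were simply wrong, the efficacy comparison would have been sized on a figure about 25 points too high.

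**Working it through.** **Inputs.** From the SAP, Aim 2: 127 per condition, alpha .025, d = .30. From the protocol: four assessments at 0, 3, 6 and 12 months. Not stated for Aim 2: sidedness, contrast, within-person correlation r. I take two-sided as the main reading and treat r as an assumption, shown at .3, .5 and .7.

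**Sample size.** 300 × .85 / 2 = 127.5, so 127 per condition corresponds to the 300 opioid-history families in protocol section B.

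**Step 1: the plan's figure as a plain two-group test.** The noncentrality is d√(n/2) = .30 × √63.5 = 2.391 on 252 degrees of freedom. Power is .555 two-sided and .663 one-sided. Detectable d at 80% power is .389 and .353. The stated >.80 is not reproduced this way.

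**Step 2: do the SAP's other power statements reproduce?** Aim 3 (r = .25, n = 127, two-tailed .05) gives .81, against a stated >.80. The pilot (50 per arm, d = .30, two-tailed .05) gives .32 as a plain comparison, against a stated <.50. Both agree.

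**Step 3: how much must the repeated measures contribute?** If a contrast has variance m times that of a single measurement, the standardised effect becomes .30/√m. Reaching .80 at 127 per condition, two-sided, needs m ≤ (.30/.389)² = .595.

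**Step 4: m for the usual contrasts**, with equal variances and a common correlation r (compound symmetry). For the slope, the squared deviations of 0, 3, 6 and 12 from their mean of 5.25 sum to 78.75, and 12² = 144.

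| Contrast | m | Power at r = .3 / .5 / .7 | r needed for .80 |
|---|---|---|---|
| Baseline-adjusted mean of 3 follow-ups | (1+2r)/3 − r² | .91 / .93 / .98 | any |
| Unadjusted mean of 3 follow-ups | (1+2r)/3 | .85 / .75 / .66 | ≤ .39 |
| Baseline-adjusted single endpoint | 1 − r² | .60 / .69 / .86 | ≥ .64 |
| Slope reaching .30 at 12 months | 144(1−r)/78.75 | .45 / .60 / .83 | ≥ .67 |
| Change score | 2(1−r) | .41 / .56 / .80 | ≥ .70 |

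For the first row, m is largest at r = 1/3, where it equals 5/9 − 1/9 = 4/9. The standardised effect is then .30/(2/3) = .45 and power is .908. This is the minimum over all r.

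**Step 5: sensitivity.** If correlation instead decays as r^(months/3), the baseline-adjusted mean of follow-ups still has power .931 / .901 / .906 at r = .3 / .5 / .7. A baseline-adjusted 12-month endpoint falls to .555 / .556 / .583.

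The thresholds above use completers only. If partial data from up to 150 per condition counted in full, which is an upper bound, the required r would fall to .54 (adjusted endpoint), .61 (slope) and .65 (change score), and the unadjusted-mean limit would loosen to .56.

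**The case for a change.** The strongest reply is that the missing inputs decide the answer. Over the five contrasts and r from .3 to .7 under compound symmetry, power runs from .41 to .98 and detectable d from .46 to .22. The statement that prior effects exceed the detectable effect is therefore true for some contrasts and false for others.

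The power sentence speaks of an overall effect, but the Aim 2 text elsewhere speaks of trajectories and of change from 3 to 12 months, which fits a slope as well as an average. The SAP states sidedness for Aim 3 and for the pilot, and a contrast for the pilot. Asking the same of the main efficacy test is not demanding.

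All of this stands as a criticism of the reporting: a reader cannot verify the Aim 2 figure from the posted text. It does not stand as evidence of an error. One ordinary analysis of the planned data supports >.80 without any favourable choice of correlation, and the section that the SAP cites for the design is not among the posted documents.

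A side issue is the 127 per condition against the protocol's 200. Protocol section B splits the 400 families into 300 and 100, and the SAP gives a 100-participant pilot its own power statement, so the two figures need not conflict. The posted text does not say whether the Aim 2 test pools all 400, but that does not bear on the power arithmetic.

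**Conclusion.** The concern does not hold as a fault in the plan. The two-group figure of .555 (detectable d = .389) is what the trial would have if the repeated measures and the baseline contributed nothing, and the SAP plans to use them. With a baseline-adjusted average over follow-up, the stated >.80 is met with room to spare: at least .908 under compound symmetry, and about .90 or more in the decaying-correlation cases checked. That result requires d = .30 to hold on average over 3 to 12 months. For a single endpoint, change score or slope, the claim would need a within-person correlation of about .64 to .70, or about .54 to .65 if partial data count in full. All correlations here are assumptions.

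What remains is a gap in reporting. Filling it would record a contrast, a sidedness and a correlation. It would not replace the planned method with a better one or correct a result that the plan would get wrong. It could not change enrolment either, since protocol section B schedules the trial phase to end in summer 2024 and the protocol is dated April 2025. Two-sided testing is the natural reading, given the SAP's other power statements.
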